## **8.0 Vulnerable Populations\***

**8.1** The research not involves individuals who are vulnerable to coercion or undue influence.

- The research not involves pregnant women.
- The research not involves neonates of uncertain viability or non-viable neonates.
- The research not involves prisoners.
- The research not involves persons who have not attained the legal age for consent (“children”).
- The research not involves cognitively impaired adults.

## **9.0 Number of Subjects**

**9.1** For the required sample size; on the basis of prior studies (Hermes et al., 2015; Dos Santos et al., 2019; Dos Santos et al., 2021), the sample size was calculated as 20 subjects per group ( $n = 40$  in total) for a significance level of 5%, a statistical power of 90%, and a difference in maximum inspiratory pressure (MIP) of at least 23 cmH2O between groups. However, to optimize the results, the required sample size was calculated as 44 participants,  $n=22$  participants per group, with consideration of a 10% loss at follow-up. Separately, after ethical approval, the ClinicalTrials.gov study registration will be done before the study starts.

## **10.0 Recruitment Methods**

**PROTOCOL TITLE:** Effects of high-intensity inspiratory muscle training as a pre-cardiac rehabilitation intervention on cardiovascular functions in patients with heart disease

For research purposes only, we propose to recruit patients that have undergone CABG surgery, history of percutaneous coronary interventions, heart failure, *and/or* myocardial infarction. Potential participants may be recruited at University of Illinois Health (UIH) clinics including Division of Cardiology ([name]). Potential participants may *actively* be recruited from the Outpatient UIH Heart Center, and the Cardiac Rehabilitation ([name]) and Exercise Testing ([name]) Programs via clinician referral during patient's routine visit.

Patients may be identified via clinician referral during routine in person visits or phone calls used to schedule a cardiac rehabilitation orientation visit. [name] and their staff may also notify [name] about whether and when any patients who meet the study criteria are scheduled to be seen in the clinic during the day or the following day. Patients that have received a referral to cardiac rehabilitation will be given the opportunity to take part in the study as long as the study requirements can be completed prior to their cardiac rehabilitation start date. Cardiac rehabilitation will not be delayed for the sole purpose of taking part in the study. Patients will not be able to do both study and cardiac rehabilitation at the same time as exercise is known to improve cardiovascular function.

The informed consent will be obtained from volunteer patients who meet the inclusion criteria. Patients will then be randomly assigned to a study or control group. The randomization sequence will generate from the [www.randomizer.org](http://www.randomizer.org) website by an investigator not otherwise involved in the study, using a table of random numbers uniformly distributed and divided into 2 groups. No names or personal identification will be given out.

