## 1.0 Study Summary

**Background / aim:** Endothelial function is closely associated with coronary artery health among individuals being treated for heart disease. An impairment in endothelial function promotes arterial stiffening that directly contributes to elevated systolic blood pressure as a result of increased vascular resistance. Inspiratory muscle training is simply a form of training consisting of repeated inspirations against a resistance. Inspiratory muscle training has also been applied to patients with chronic disease or as an additional therapy for cardiac rehabilitation and it has proven to be safe in these groups. Few studies in the literature examined the effects of high intensity inspiratory muscle training in this population, however, these studies did not examine the direct effects of inspiratory muscle training on vascular function. To the best of our knowledge, the effects of inspiratory muscle training in patients with heart disease on endothelial function and arterial stiffness prior to starting cardiac rehabilitation have not been investigated.

**Methods:** The study was designed as a randomized controlled trial. The demographic and clinical characteristics of the patients will be recorded after consent is obtained from the volunteer patients who meet the inclusion criteria. Subsequently, patients will be randomly divided into two groups (22 subjects in each group) for inspiratory muscle training (IMT) with 60% of maximum inspiratory pressure (MIP) or sham inspiratory muscle training (Sham-control), for 4 weeks. In both groups, before and after 4-week-training, resting blood pressure (systolic/diastolic), resting heart rate, endothelial function, arterial stiffness, functional exercise capacity, the severity of dyspnea and inspiratory muscle functions will be measured.

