### **11.1 Assessments**

#### **11.1.1 Evaluation of mental state (visit #1)**

**PROTOCOL TITLE:** Effects of high-intensity inspiratory muscle training as a pre-cardiac rehabilitation intervention on cardiovascular functions in patients with heart disease

A standardized Mini Mental Test (SMMT) will be used to evaluate the mental state. SMMT is a test with high sensitivity levels for moderate to severe cognitive impairment, as well as satisfactory reliability, internal consistency, and test-retest reliability, first developed by (Folstein et al., 1975) (Tombaugh & McIntyre, 1992). The test, which is one of the most widely used screening criteria for evaluating neuropsychological functions, is used in many patient groups, including heart diseases. SMMT is a scale that evaluates cognitive functions in orientation, registration, attention and calculation, recall and language sub-categories with a total of 30 points. Low scores indicate poor performance, while the cut-off point of the test is 24 for most patient populations (Nussmeier et al., 2010; Tombaugh and McIntyre, 1992). In our study, individuals who score below 24 in SMMT will be excluded from the study. The SMMT attached end of this document.

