#### **11.1.2 Questioning alcohol use (visit #1)**

The alcohol use status of the participants will be evaluated by the American Psychiatric Association, Diagnostic and Statistical Manual of Mental Disorders (DSM-5) (American Psychiatric Association, 2013). The DSM-5 evaluates an individual's alcohol use in the last 12 months with 11 items. Under the DSM-5, individuals who meet any 2 of 11 criteria within the last 12 months are diagnosed with alcohol dependence. The severity of the addiction (mild, moderate, or severe) depends on the number of criteria met. Participants meeting 2 or more of the 11 criteria defined in the DSM-5 in our study will be excluded from the study. The DSM-5 attached end of this document. Alcohol consumption is known to affect vascular function.

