## **24.0 Setting**

This research will take place in the Physical Therapy Faculty Practice located at [name] in Chicago.

Informed consent and authorization will be obtained after eligibility screening has been confirmed, either during the routine patient visit at the outpatient Exercise Testing or Cardiac Rehabilitation Programs.

Subjects expressing interest in participating in the study will communicate to key research personnel conducting the screening and consenting process. During the routine visit, oral consent will be obtained so that eligibility screening.

An alteration of consent and a waiver of documentation of consent will be obtained for the eligibility screening.

All investigators/study personnel carrying out recruitment will follow a detailed informed consent process that will include a careful review study requirements and explanation of the study protocol

PI, and Key Research Personnel (research assistants) will obtain consent. Beside the PI and Co-Is, study staff thoroughly trained by the PI in the consenting process, and who have completed their CITI and HIPPA training may also obtain consent from subjects.

After consent obtaining the first appointment for baseline measurements will be determined and research procedures detailed in section 11.0 will be carried out.

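### The protocol does not place randomisation after the visit-1 exclusion checks and baseline tests, its sections conflict on the order, and no step conceals the assignment until then

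*Protocol*

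**What the plan says.** **Randomisation.** Protocol section 10.0 gives two consecutive steps: "The informed consent will be obtained from volunteer patients who meet the inclusion criteria", then "Patients will then be randomly assigned to a study or control group". An investigator with no other role generates the sequence. The section does not say who holds the list or when an assignment is disclosed.

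**Baseline visit.** Section 24.0 makes this a separate, later step: "After consent obtaining the first appointment for baseline measurements will be determined". Sections 11.1.1 to 11.1.7 label every assessment as visit #1: mental state, alcohol use, dyspnoea, the 6-minute walk test (6MWT), inspiratory muscle function including maximal inspiratory pressure (MIP), flow-mediated dilation (FMD) and pulse wave velocity (PWV).

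**Exclusions made at that visit.** Section 11.1.1: "individuals who score below 24 in SMMT will be excluded from the study". Section 11.1.2: "Participants meeting 2 or more of the 11 criteria defined in the DSM-5 in our study will be excluded from the study". The mini-mental (SMMT) cut-off also appears in list 7.2; the alcohol criterion does not.

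**Text pointing the other way.** The Study Summary puts a step between consent and randomisation: "The demographic and clinical characteristics of the patients will be recorded after consent is obtained from the volunteer patients who meet the inclusion criteria", followed by "Subsequently, patients will be randomly divided into two groups". Section 11.0 labels demographics and past medical history as visit #1 data. Sections 11.0, 22.0, 23.0 and 24.0 say eligibility is determined before written consent.

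**Analysis.** Protocol section 17.1 plans ANCOVA with the baseline as covariate. The SAP plans analysis of variance on change from baseline. Both use the visit-1 value.

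**The concern.** If randomisation comes first and the arm is known, two things can go wrong.

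- **Exclusions after allocation.** A patient who fails the mini-mental or alcohol check at visit 1 would already have an arm. If these exclusions depend on the arm even slightly, the groups compared are no longer the groups randomised. Neither document defines an analysis population that would deal with such patients.
- **Baselines coloured by the arm.** MIP is a primary endpoint and the basis of the sample size in section 9.1. MIP and the walk test both depend on effort and so on encouragement. If coaching at baseline differs by arm, part of that difference enters the estimated treatment effect, and the analysis cannot remove it afterwards.

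The sham device may mask patients. It does not mask staff who set a load in one arm and none in the other. Section 25.1 describes one full-time person who oversees visits and collects data, and assessor blinding is not mentioned anywhere.

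**Working it through.** **1. The order of steps, side by side**

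| Source (Protocol) | Order it supports |
|---|---|
| 10.0 | Consent, then randomisation |
| 24.0, baseline appointment | Consent, then visit 1 is booked |
| 11.1.1, 11.1.2 | Exclusion checks at visit 1 |
| 11.1.3 to 11.1.7 | All outcome baselines at visit 1 |
| 1.0 with 11.0 | Consent, some visit-1 data, then randomisation |
| 11.0, 22.0, 23.0, 24.0 | Eligibility settled, then written consent |

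The first four rows together give randomisation before visit 1. The fifth allows randomisation during visit 1. The sixth would put the SMMT check before consent, which contradicts its visit #1 label. It does not clearly reach the alcohol criterion, which is missing from 7.2. No row puts randomisation after the exclusion checks and outcome baselines.

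**2. The plan's own sample size**

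Section 9.1 gives 20 per group for a 23 cmH2O difference in MIP, 5% significance and 90% power. It gives no SD, so the figure cannot be reproduced. Solving the two-sided t-test (noncentral t, 2n - 2 degrees of freedom, noncentrality 23 / (SD x sqrt(2/n))) for 90% power at n = 20 gives SD of about 21.9. This back-solved value is an assumption below. The allowance for loss is 20 x 1.10 = 22, as stated.

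**3. Power if patients are excluded after randomisation** (exclusion rates assumed)

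| Excluded | Left per arm after 10% loss | Power |
|---|---|---|
| 0% | 22 x 0.90 = 19.8 | 89.7% |
| 5% | 22 x 0.95 x 0.90 = 18.8 | 88.1% |
| 10% | 22 x 0.90 x 0.90 = 17.8 | 86.2% |

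**4. False-positive rate if the baseline shifts with the arm**

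Assumptions: no true effect; 20 analysed per arm; SD 21.9 at each visit; baseline-final correlation r of 0.5 to 0.8; a between-arm shift b in measured baseline MIP that does not carry over to the final measurement.

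- Change score (SAP): bias = b; SD = 21.9 x sqrt(2(1 - r)), which is 21.9 at r = 0.5 and 13.8 at r = 0.8.
- ANCOVA (Protocol 17.1): bias = r x b; residual SD = 21.9 x sqrt(1 - r^2), which is 18.9 at r = 0.5 and 13.1 at r = 0.8.
- Standard error = SD x sqrt(2/20). The rejection probability is that of a two-sided 5% test whose true mean equals the bias.

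Example, b = 5 and r = 0.5. Change score: standard error 6.91, bias/standard error 0.72, rejection about 11%. ANCOVA: bias 2.5, standard error 5.99, ratio 0.42, rejection about 7%.

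| Shift b (cmH2O) | Change score, r = 0.5 to 0.8 | ANCOVA, r = 0.5 to 0.8 |
|---|---|---|
| 1 | 5-6% | about 5% |
| 2.5 | 6-9% | 5-8% |
| 5 | 11-20% | 7-16% |

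A shift of 5 is 5/23 = 22% of the planned difference. The change score carries all of it; ANCOVA carries 2.5 to 4.0 cmH2O, or 11-17%.

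**The case against.** The strongest reply is that section 10.0 is a short recruitment narrative, not a schedule. The Study Summary has data recorded before randomisation, and section 11.0 makes those data part of visit 1, so on the protocol's own labels some of visit 1 may come first. The SMMT cut-off is in list 7.2, and four sections settle eligibility before written consent, so that exclusion may well be complete before anyone is randomised. The sequence is generated independently, the two exclusions use numeric cut-offs that leave limited discretion, and the familiarisation session on the baseline day is unloaded in both arms.

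Much of this stands. A reader might infer that the protocol definitely randomises before all visit-1 testing and that staff know the arm when they exclude or test patients. The documents do not support that: the order is the most direct reading of sections 10.0 and 24.0 but is contradicted elsewhere, and knowledge of the arm is not stated, only not ruled out. A reader might also infer that every planned analysis passes a baseline shift on in full. That is true of the change score but not of ANCOVA.

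What the reply does not supply is any text placing randomisation after the exclusion checks and outcome baselines, or withholding the assignment until then. Independent generation of a list is not concealment of it. The alcohol criterion also lacks the support that list 7.2 gives the SMMT.

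**Conclusion.** The concern holds as a gap and a conflict in the plan, not as proof of biased conduct. Staff who followed sections 10.0 and 24.0 literally would randomise before the exclusion checks and baselines, and nothing written would stop the assignment from reaching them.

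The loss of power is minor. The possible bias matters more, but its size is unknown: negligible for a 1 cmH2O shift, and a false-positive rate of about 11-20% (change score) or 7-16% (ANCOVA) for a 5 cmH2O shift. These figures rest on the back-solved SD and on assumed shifts and correlations; neither document gives any of them. The change should be made because it is cheap and the bias cannot be repaired later.

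**What to change.** - State one order in Protocol sections 1.0, 10.0, 11.0 and 22.0 to 24.0: consent; visit-1 exclusion checks (SMMT and DSM-5 alcohol criteria); all baseline measurements; randomisation.
- Have the uninvolved investigator who generates the list also hold it, and release each assignment only after that patient's baseline record is complete.
- Add the alcohol criterion, which section 11.1.2 already applies, to list 7.2.
- Reconcile the statements that eligibility is confirmed before consent with the visit #1 labels on the SMMT and alcohol checks.

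The cost is protocol wording and one hand-off at the end of visit 1. Because the familiarisation session is the same in both arms, nothing described for visit 1 needs the assignment earlier.

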## **11.0 Procedures Involved\***

This research will take place in the Physical Therapy Faculty Practice located at [name] in Chicago, IL. It will be an interventional randomized controlled study. The data will be collected for research purposes only. We will ensure to participants that no new information (i.e., results from any study procedures) will be entered into or collected from patient's medical records. After eligibility is determined, those who agree to participate (provide oral consent) will be required to provide written informed consent statement before proceeding to subsequent data collection. All participants, both control and intervention, will be assessed with the following assessments.

Baseline Clinical Data collected will include demographics, level of educational attainment and past-medical history. Anthropometrics, Body Mass (kg) and height (m) will be assessed. (**visit #1**)

### **11.1 Assessments**

#### **11.1.1 Evaluation of mental state (visit #1)**

**PROTOCOL TITLE:** Effects of high-intensity inspiratory muscle training as a pre-cardiac rehabilitation intervention on cardiovascular functions in patients with heart disease

A standardized Mini Mental Test (SMMT) will be used to evaluate the mental state. SMMT is a test with high sensitivity levels for moderate to severe cognitive impairment, as well as satisfactory reliability, internal consistency, and test-retest reliability, first developed by (Folstein et al., 1975) (Tombaugh & McIntyre, 1992). The test, which is one of the most widely used screening criteria for evaluating neuropsychological functions, is used in many patient groups, including heart diseases. SMMT is a scale that evaluates cognitive functions in orientation, registration, attention and calculation, recall and language sub-categories with a total of 30 points. Low scores indicate poor performance, while the cut-off point of the test is 24 for most patient populations (Nussmeier et al., 2010; Tombaugh and McIntyre, 1992). In our study, individuals who score below 24 in SMMT will be excluded from the study. The SMMT attached end of this document.

#### **11.1.2 Questioning alcohol use (visit #1)**

The alcohol use status of the participants will be evaluated by the American Psychiatric Association, Diagnostic and Statistical Manual of Mental Disorders (DSM-5) (American Psychiatric Association, 2013). The DSM-5 evaluates an individual's alcohol use in the last 12 months with 11 items. Under the DSM-5, individuals who meet any 2 of 11 criteria within the last 12 months are diagnosed with alcohol dependence. The severity of the addiction (mild, moderate, or severe) depends on the number of criteria met. Participants meeting 2 or more of the 11 criteria defined in the DSM-5 in our study will be excluded from the study. The DSM-5 attached end of this document. Alcohol consumption is known to affect vascular function.

#### **11.1.3 Dyspnea Evaluation (visit #1, 4-week visit)**

The modified Medical Research Council (mMRC) dyspnea scale used in the evaluation of general dyspnea is a simple, valid and reliable five-item scale based on various physical activities that cause dyspnea. With this scale, patients are asked to mark the activity level that causes dyspnea (Bestall et al., 1999). There are many studies indicating that this scale is associated with dyspnea, arterial blood gases, health status, and lung function tests (Bausewein et al., 2007; Bestall et al., 1999; Wilson and Jones, 1989). The mMRC dyspnea scale attached end of this document.

#### **11.1.4 Evaluation of Functional Exercise Capacity (visit #1, 4-week visit)**

Submaximal functional exercise capacity will be evaluated with the 6-minute walking test (6MWT). 6MWT is a test that is frequently used in the evaluation of submaximal functional exercise capacity, has a low cost, provides important clinical results and is recommended by the guidelines

**PROTOCOL TITLE: Effects of high-intensity inspiratory muscle training as a pre-cardiac rehabilitation intervention on cardiovascular functions in patients with heart disease**

(ATS, 2002). As the standard protocol of the test, the person is asked to walk as fast as possible for six minutes in a continuous 30-meter corridor. Peripheral oxygen saturation, heart rate, perceived severity of dyspnea and leg fatigue (range 0-10) with the modified Borg scale are recorded before and after the test (ATS 2002; Borg, 1982). At the end of the test, the total distance walked is recorded in meters (Enright and Sherrill, 1998).

**11.1.5 Inspiratory Muscle Function Evaluation (visit #1, 2-week visit, 4-week visit)**

Inspiratory muscle function testing will be obtained from the PrO2Fit device (PrO2 Health Incorporated, Rhode Island, NE, USA) in which the maximal inspiratory pressure (MIP), total breath power and Fatigue Index Test (FIT) can be seen (McCreery et al., 2021). The PrO2Fit device incorporates a 2 mm leak to avoid glottal closure during maximal inspiration. The MIP is the highest pressure measured during inspiration and measured at residual volume (RV), with the unit of measure centimetres of water (cm H2O).

**11.1.6 Endothelial Function Assessment (visit #1, 4-week visit)**

A standard non-invasive method will be used to assess endothelial function. For this, flow-mediated dilation (FMD) ultrasound measurements of brachial artery flow-mediated dilatation will be performed according to standard methods with ultrasonography (ProSound α7; Aloka, Tokyo, Japan) using a multifrequency linear array transducer as previously described (Ozemek et al., 2020; Thijssen et al., 2011). Briefly, a cuff will be placed on the upper forearm and brachial artery images will be taken ~3–6 cm above the antecubital fossa. After taking simultaneous measurements of 1-min baseline brachial artery diameter and blood flow velocity, forearm occlusion will be produced by inflating the cuff to 250 mmHg for 5 minutes and then rapidly deflating it. After the release of the artery occlusion, Doppler blood flow velocity will be obtained and B-mode ultrasound brachial artery diameter images will be measured continuously for 3 minutes. Brachial artery diameter and blood flow velocity will be analyzed using an available software package (QUIPU SRL, Cardiovascular Suite 4.5.0, Italy). All procedures will be performed following published guidelines for the assessment of FMD in human participants (Corretti et al., 2002; Thijssen et al., 2011).

**11.1.7 Evaluation of Arterial Stiffness (visit #1, 4-week visit)**

Arterial stiffness will be assessed by measuring pulse wave velocity with a dedicated system (Noninvasive hemodynamics (NIHem) workstation, Cardiovascular Engineering, Inc. Norwood, MA) according to the methods

**PROTOCOL TITLE:** Effects of high-intensity inspiratory muscle training as a pre-cardiac rehabilitation intervention on cardiovascular functions in patients with heart disease

previously described (Mitchell et al., 2010). Arterial tonometry of the brachial, radial, femoral and carotid artery will be performed with a custom transducer and waveforms were signal-averaged and gated to the ECG R-wave (NIHem, Cardiovascular Engineering, Inc. Norwood, MA) as previously described (Mitchell et al., 2010). Measurements will be made after a four-hour fast and before any other exercise test to be performed on the same day (Scalzo et al., 2017; Mitchell et al., 2010).

